5.4 Study procedures

Participants expressing interest will first complete an initial online screening form (e.g., via FormSG or Microsoft Forms), containing non-sensitive questions to assess eligibility based on study criteria such as English proficiency, age, meditation experience, vision and hearing capabilities, willingness to commit to the study procedures, and any relation to A*STAR research team members. Participants will also provide their phone number, which will be used to notify them of their eligibility status. The phone number will be retained until the end of data collection to prevent repeat participation, facilitate the delivery of study materials, and ensure compensation via e-vouchers. The study coordinator will check whether a mobile number has been previously used and stop participants if a duplicate number is detected.

Once the study coordinator reviews the responses daily, eligible participants (i.e., those meeting inclusion and exclusion criteria and those who provided a phone number not previously entered in the survey), will receive a standardized text

message (e.g., via WhatsApp) confirming their preliminary eligibility. For ineligible participants, their collected data will be discarded. If eligible, participants will be informed that the study will begin within three weeks. Upon the recruitment of the 20th participant or at the end of the third week, the coordinator will notify the cohort, instructing them to start the study within two days. The study will consist of three cohorts of 20 participants each. If fewer than 60 participants are recruited after the third cohort, an additional cohort will be organized to reach the target number.

At this point, participants will receive a message containing the following: a link to access the Qualtrics survey, an access code (which serves as an anonymous identifier), and a link to instructions for downloading the 'Camera Heart Rate Variability' app, used for heart rate variability (HRV) measurement. The instructions will detail how to take measurements and submit the generated HRV.csv data files to the study team. Participants will also receive a code to download the app for free. They will be advised to complete the survey each day at the same time, between 9 am and 9 pm.

The Qualtrics link contains the written informed consent form and the actual experiment. Participants will be able to review all relevant information about the study and either accept or decline to participate. If they do not provide consent, they will be opted out of the study. If consent is provided, participants will proceed to the second screening, which involves answering additional questions about their use of concomitant medication. If they meet the criteria for this stage, they will proceed to answer questions about any neurological or psychiatric conditions. If any of the screening criteria are not satisfied at any point, the study will automatically terminate. Once consent and second screening are complete, participants will then be instructed to move to a quiet environment where they will not be disturbed for the next 35 minutes. They will be asked to download the 'Camera Heart Rate Variability' app and take an initial HRV measurement for testing purposes. Participants will then submit the generated CSV file to the study coordinator via WhatsApp and self-report their rMSSD values in the Qualtrics survey. Participants are instructed to label their CSV files using their anonymous identifier provided by the study coordinator via WhatsApp at the start. Afterward, they will complete a series of questionnaires, including the 20-item IPIP scale, the RS-14, the FFMQ, and various demographic questions such as age, gender, ethnicity, smartphone type used during the experiment, and its operating system (iOS or Android) and version. Pre-intervention assessments of STAI-6, EMA will also be conducted. They will then use the 'Camera Heart Rate Variability' app to measure HRV, submit the generated CSV file to the study coordinator, and self-report their rMSSD values in the Qualtrics survey, as outlined in the instructions.

Participants will then be randomly assigned by the Qualtrics engine to either the experimental group, which listens to a mindfulness audio track, or the control group, which listens to a 'sham meditation' track. Both tracks are embedded within the Qualtrics survey. Participants cannot skip this portion of the survey for 10 minutes, ensuring they listen to the entire 10-minute audio track. Afterward, participants will be asked to sit quietly for three minutes without engaging in any activities. This pause is necessary because, some of the audio track encompasses the application of mindfulness principles while performing a routine activity (e.g., brushing teeth) during the listening of a mindfulness track. Although the movement involved in this activity is minimal, we want participants to sit still for three minutes to avoid introducing any confounding variables in the subsequent HRV assessments. The survey will be programmed to remain stuck during this period to prevent participants from skipping this step.

Following the quiet period, participants will complete post-intervention assessments for STAI-6, EMA and HRV. Participants will be thanked and instructed to reopen the survey link the following day, ideally at the same time between 9am and 9pm. On Day 2, they will complete the same pre-intervention assessments (STAI-6, EMA and HRV), listen to a different audio track, either mindfulness or sham meditation, depending on their group allocation, sit for three minutes, and then complete the post-intervention assessments mirroring Day 1. On Day 3, participants will undergo the same procedure as Day 2 but will listen to another audio track (mindfulness or sham). Additionally, they will complete the FFMQ, answer questions about their expectations of the intervention, its credibility, the PARH scale, and the usability questionnaire. Finally, participants will be thanked for their participation in the study and debriefed.

6. Ethics information

This study will be conducted in accordance with the ethical principles outlined in the Declaration of Helsinki and in compliance with applicable regulatory requirements. The final study protocol, along with the latest version of the Participant Information and Consent Form, will receive written approval from the A*STAR Institutional Review Board (A*STAR IRB) before any participants are enrolled.

Participants who express interest in the study will first complete an initial screening, where non-sensitive questions will be asked to assess their English proficiency, age, meditation experience, vision and hearing capabilities, willingness to commit to study procedures, and any relation to A*STAR research team members. If participants do not meet the inclusion/exclusion criteria at this stage, their responses will be promptly disposed of to ensure anonymity. If they qualify, they will be sent a link to the Qualtrics platform, which will contain the written informed consent form and the actual experiment.

Given that the study poses minimal risk to participants, does not involve the use of medication, and is not expected to result in any incidental findings, we will implement a written informed consent process. Participants will be able to review all relevant information about the study and provide their consent through the online survey used for the experiment. A study coordinator and witness will not be present during the consent process. If participants choose not to consent, they will be opted out of the study. Those who do provide consent will be asked additional questions regarding their use of concomitant medication. If the participant satisfies this inclusion criteria he will pass at the next window of the survey where he will answer a question related to neurological or psychiatric conditions. If any screening criteria are not satisfied, the study will automatically terminate at that point.

As part of standard ethical procedures, participants will provide their consent by completing a written form administered through the online survey platform. We will collect participants' phone numbers to facilitate compensation and to prevent multiple survey submissions. All phone numbers will be deleted at the end of the trial.

Although participants will email the study coordinator with the generated CSV file, their email addresses will not be collected, and once the CSV file is downloaded, the email will be permanently deleted. All other data collected will be de-identified to protect participants' anonymity.

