The first HRV measurement will serve as testing purposes and will be taken immediately after the survey that will prompt participants to go to a quiet place just after the start of the experiment. The additional HRV measurements will be taken twice daily, immediately following the completion of each Ecological Momentary Assessment (EMA).

One-time measurement (end of the trial)

Usability of the intervention to assess the usability of the current pilot trial, a set of questions will be asked to assess the participants' experiences with the mindfulness and sham meditation tracks in terms of ease of use, clarity of instructions, relevance to daily life, engagement levels, comfort, perceived efficacy, willingness to continue usage, any technical issues encountered, and suggestions for improvement.

Perceived Awareness of the Research Hypothesis (PARH; Rubin 2016) is a four-item quantitative self-report tool designed to assess the possible impact of demand characteristics in research settings. Its purpose is to assist in challenging the notion that observed effects can be attributed to demand characteristics. Participants provide their responses to these statements using a 7-point Likert-type scale, where the options range from strongly disagree (1) to strongly agree (7). Examples of statements include: "I was aware of the researchers' objectives in this study" and "I was uncertain about the researchers' intentions in conducting this research".

Expectancy and credibility of the intervention

To assess expectancy, we will use a single item adapted from the Credibility/Expectancy Questionnaire (Devilly & Borkovec, 2000) during the final phase of post-intervention testing: "On a scale from 0 to 10, How effective do you believe the meditation training has been in alleviating stress? (0 = Not at all successful, 10 = Extremely successful)."

To evaluate credibility, participants will respond to a two-part question: "If you were informed that you might have received either meditation training or control training, which type do you believe you received? (Meditation, Control)". "How confident are you in your answer? (0 = Not at all confident, 10 = Extremely confident)".

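### The Day 3 order of the end-of-trial scales is unsettled, and the order listed in section 5.4 would put two cueing items just before PARH, the only measure of hypothesis awareness

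*Combined protocol and SAP*

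**What the plan says.** Section 5.4 is the only step-by-step account of Day 3. Beyond the daily assessments and the third track, it says "they will complete the FFMQ, answer questions about their expectations of the intervention, its credibility, the PARH scale, and the usability questionnaire", after which participants are thanked and debriefed.

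The end-of-trial part of section 5.3.2 gives the content of these scales:

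- Expectancy is a single item, placed "during the final phase of post-intervention testing". It asks "How effective do you believe the meditation training has been in alleviating stress".
- Credibility is a forced choice: "If you were informed that you might have received either meditation training or control training, which type do you believe you received", followed by a confidence rating.
- PARH has four items on a 7-point scale and is "designed to assess the possible impact of demand characteristics in research settings". One of its two example items is "I was aware of the researchers' objectives in this study".
- Usability covers, among other things, how effective participants felt the tracks were.

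In section 8.2 the credibility and awareness responses form one exploratory analysis, used to judge whether the two conditions were equally credible. No method is named, and item order is not mentioned.

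**The concern.** PARH asks people to look back and say whether they knew what the researchers were after. Its value depends on the survey not having told them just beforehand. In the section 5.4 list, the expectancy item links the training to relief of stress, and the credibility item then raises the possibility of a control training and makes the participant guess an arm. PARH follows directly.

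A high PARH score could then mean awareness during the three days, or awareness picked up in the previous minute. A PARH difference between arms could arise from the guess just made. There is no other awareness score to compare with, so the analysis could not separate these explanations afterwards.

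This matters because section 5.3.2 says of PARH: "Its purpose is to assist in challenging the notion that observed effects can be attributed to demand characteristics". Section 2 also says that participants' feedback on the pilot will be used to refine the method for a larger decentralised study, so an unsuitable order could be carried forward.

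**Working it through.** No figure in the plan bears on this. The check sets the sections side by side.

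**1. The two orders**

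| Place | Section 5.4, Day 3 | Section 5.3.2, end of trial |
|---|---|---|
| 1 | FFMQ | (FFMQ is described separately, with the pre and post measures) |
| 2 | Expectancy | Usability |
| 3 | Credibility | PARH |
| 4 | PARH | Expectancy |
| 5 | Usability | Credibility |

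The four scales common to both lists form 4 × 3 / 2 = 6 pairs. Only one pair (expectancy before credibility) has the same order in both. The other 5 are reversed, including both pairs that matter here: expectancy with PARH, and credibility with PARH. Neither section says that its order is the order of administration.

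**2. What precedes PARH if section 5.4 is followed**

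The expectancy item ("How effective do you believe the meditation training has been in alleviating stress") names the effect sought. The credibility item ("If you were informed that you might have received either meditation training or control training, which type do you believe you received") raises a control condition and asks for a guess. PARH then asks for agreement with statements such as "I was aware of the researchers' objectives in this study". Both cues concern what PARH is meant to measure.

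**3. What participants had already seen**

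The EMA includes an item on feeling stressed. It is given twice a day for three days, so 2 × 3 = 6 times before the end-of-trial scales. Stress as a topic is therefore not new. However, that item is one of seven state items, alongside fatigue, mood and sleep, and it does not say that the training is meant to reduce stress. The expectancy item makes that link.

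Whether a control arm is already known depends on the consent form, which is not in the documents available. The conditional wording of the credibility item and the sham's design in section 5.2.2, which aims to pass for real meditation, are consistent with non-disclosure. They do not prove it.

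**4. Which measures are exposed**

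Post-track STAI-6, EMA and HRV are described as following the three-minute quiet period. FFMQ comes first in the section 5.4 list. On that sequence none of them follows a cueing item. PARH does. Usability would also come after the arm guess.

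**5. How many participants**

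Everyone who completes Day 3 would be exposed. With 60 recruited and about 20% dropout, 60 × 0.80 = 48; the plan's own target is at least 50. The documents give nothing from which to estimate how far the cues would move a PARH score.

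**The case against.** The strongest reply is that the order is only inferred. Section 5.4 presents the scales as an addition, in one sentence with no word marking sequence, although the same section does mark sequence elsewhere. Section 5.3.2 is compatible with PARH coming before expectancy and credibility. This stands. The secure finding is that the two listings disagree and the order is not fixed, and that the section 5.4 order is the one with the problem.

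Other points carry weight:

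- A reader might infer that PARH would be worthless. The documents do not support that. The example items are in the past tense and ask about awareness in the study, and a shift common to both arms may partly cancel when arms are compared. The score is open to contamination, not void. The cancelling is only partial, because arm guesses may differ by arm.
- A reader might infer that the credibility item is the first disclosure of a control arm. Without the consent text that cannot be established. Even if a control was disclosed earlier, a forced guess just before PARH could still influence the answers.
- A reader might infer that the trial's outcomes are contaminated. The described sequence points the other way, as shown in step 4.
- The stakes are limited. PARH is exploratory, the sham arm is the main design control for demand, and section 1 can be read as assigning the question of genuine versus expectation-driven effects mainly to the later multi-site study.
- Order effects run both ways: asking about the hypothesis first could influence the later arm guess. That is a real trade-off. Putting PARH first is still preferable, since the PARH examples shown do not mention a control condition, whereas the credibility item does.

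**Conclusion.** The concern holds in limited form. The plan gives two incompatible listings of the end-of-trial scales and fixes neither. If the survey follows section 5.4, the single PARH score would be taken straight after one item linking the training to stress relief and another raising a possible control training. It could then partly reflect those items and the arm guess.

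All completers, about 48 to 50 of 60, would be exposed. The size of the shift is unknown. Higher reported awareness is the plausible direction, but the documents do not establish it.

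The conclusion assumes that the survey is built in the section 5.4 order, and its force depends partly on what the consent form says about a control arm. It does not extend to STAI-6, EMA, HRV or FFMQ. The change is worth making before data collection, because the contamination could not be undone afterwards.

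**What to change.** Reconcile sections 5.3.2 and 5.4, and state in section 5.4 that the Day 3 Qualtrics order is fixed as follows:

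1. post-track STAI-6, EMA and HRV;
2. FFMQ;
3. PARH;
4. usability;
5. expectancy;
6. the meditation-or-control guess, with confidence;
7. debrief.

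Block back-navigation to PARH. PARH should precede usability as well as expectancy, because the usability questions also ask about perceived efficacy and so carry a similar cue. This order also keeps the usability ratings ahead of the arm guess.

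The cost is a reordering of survey blocks and a short edit to the two sections, with no extra items, participant time or sample size. PARH would remain a single recall measure at the end of the trial: it could not date awareness to Day 1 or Day 2, and the report should say so.

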6.2 Data protection

Data will be processed in accordance with the Data Protection Act 2018 and the General Data Protection Regulation 2016 (GDPR). All information collected will be kept strictly confidential. The data we will collect for this study will be made anonymous from the start. All electronic data will be stored on password-protected computers belonging to the research team. The researchers will abide by local data protection laws when collecting personal data. All research data will be captured as de-identified (coded) electronic data. A designated folder will be created for the study team to store the research data files on an SOD (Storage on demand) space. The A*STAR SOD is created on secured A*STAR servers and is designed with strict access controls. Once the data is no longer necessary (maximum of 10 years), it will be appropriately discarded (e.g., deleted off from A*STAR's SOD).

7. SAFETY MEASUREMENTS

7.1 Definitions

Serious adverse event (SAE) in relation to human biomedical research means any untoward medical occurrence because of any human biomedical research which:

- Results in or contributes to death
- Is life-threatening
- Requires inpatient hospitalization or prolongation of existing hospitalization
- Results in or contributes to persistent or significant disability/incapacity
- Results in or contributes to a congenital anomaly /birth defect
- Results in the transmission of a communicable disease
- Results in any misidentification or mix-up of any type of tissue, gametes or embryo
- Any other events that may be prescribed

7.2 Safety Monitoring Plan

The Principal Investigator (PI) will collect feedback from participants at the end of the trial. Given that this study involves minimal risk to participants and does not include the use of medications, we do not plan to systematically record adverse events. Therefore, we do not anticipate significant risks of adverse events.

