4.5. Participant discontinuation criteria

The participant has the right to withdraw from the trial at any time without facing any negative consequences.

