7.4. Complaint Handling

Any feedback from participants of each site will be taken seriously and concerns will be brought up to the PI to follow up.

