8. SAMPLE SIZE AND STATISTICAL METHODS

8.1. Determination of Sample Size.

Since this is a pilot trial, we aim to recruit 60 participants to account for a ~20% dropout rate, ensuring we meet our target of at least 50 participants.

8.2. Statistical analyses.

Our confirmatory statistical analyses will include:

- Bayesian mixed-effects models to investigate the longitudinal changes in self-reported stress measured via STAI-6. The model will have STAI-6 as the

dependent variable, with 'Group' (mindfulness intervention or control), 'Day' (1 to 3), and their interaction term as independent variables. Participant ID will be used as a random intercept to control for individual differences. A BF10 greater than 1 will indicate slightly positive evidence supporting the effectiveness of the mindfulness condition over the control condition in stress reduction.

We will also conduct the following exploratory statistical analyses:

- A Bayesian mixed-effects model to assess longitudinal changes in HRV, using HRV as the dependent variable and 'Group', 'Day' (1 to 3), and their interaction as independent variables. Participant ID will again serve as a random intercept. A BF10 greater than 1 will suggest positive evidence for the mindfulness intervention's effectiveness compared to the control.
- An additional Bayesian mixed-effects model will analyze longitudinal changes in HRV, with the dependent variable being HRV (calculated by the difference in pre- and post-meditation HRV scores) and independent variables including 'Group', 'Day' (1 to 3), and their interaction. Participant ID will account for individual variability in baseline HRV levels.
- Correlational analyses to explore the relationship between changes in mindfulness scores and stress levels, as well as between HRV changes and stress levels.
- Descriptive statistics to summarize baseline participant characteristics, such as neuroticism, RS-14 scores, FFMQ scores related to mindfulness training, and demographic details.
- Analysis of responses regarding the intervention's credibility and participant awareness of the research hypothesis to assess equal credibility of the intervention for the mindfulness condition and the sham.

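### The plan defines no adverse event count by arm, and participants who stop after hearing a track are not asked about unwanted effects

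*Combined protocol and SAP*

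**What the plan says.** Section 7.2 states the safety plan in three sentences. The first sets the enquiry: "The Principal Investigator (PI) will collect feedback from participants at the end of the trial". The second cites minimal risk and the absence of medication, then says "we do not plan to systematically record adverse events". The third concludes: "Therefore, we do not anticipate significant risks of adverse events".

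The sections around it add the following:

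- Section 7.1 defines a serious adverse event, beginning "Serious adverse event (SAE) in relation to human biomedical research means any untoward medical occurrence because of any human biomedical research which", and lists the qualifying outcomes. It gives no step for detecting or reporting one.
- Section 7.4 handles complaints: "Any feedback from participants of each site will be taken seriously and concerns will be brought up to the PI to follow up". It sets no time limit, form or link to arm.
- Section 4.5 reads in full: "The participant has the right to withdraw from the trial at any time without facing any negative consequences". It mentions neither a reason for stopping nor a contact on exit.
- Section 5.3 lists the topics of the end-of-trial usability questions. Comfort and technical problems are among them; unwanted effects are not. Section 5.4 places this questionnaire on Day 3.
- Section 8.1 sets recruitment at 60 "to account for a ~20% dropout rate", with at least 50 to remain.
- Section 8.2 lists no safety tabulation.

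**The concern.** Section 1 presents the pilot as the groundwork for a randomised multi-site study, and section 2 says it should refine the method for a larger, fully decentralised one. Whether unwanted effects can be collected remotely, including from people who stop, is something such a pilot could find out at almost no cost. As written, it will end with no defined numerator in either arm and no question put to those who leave early.

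The wording of section 7.2 adds a smaller problem. The sentence opening with *Therefore* follows directly on the decision not to record, so low risk reads as though it followed from not looking. The reasons that could support the expectation are the minimal-risk argument and the literature summary in section 3.

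**Working it through.** **Inputs.** Section 8.1 gives 60 recruited, about 20% dropout and at least 50 remaining. Section 3 gives cited adverse event rates of 1% (mindfulness) and 0.9% (control), and six intervention-related events among 1231 MBSR participants. The allocation ratio is not stated; 1:1, or 30 per arm, is assumed below.

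**The plan's own figures.** 50 × (1 + 0.20) = 60, which reproduces the recruitment target. Run forward, 60 × (1 − 0.20) = 48, slightly under 50. The cited MBSR rate is 6/1231 = 0.49%, as stated.

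**How many might not be asked.** At 20% dropout, 60 × 0.20 = 12. If exactly 50 remain, 60 − 50 = 10. Both are upper figures, because they take every loss to occur after a track has been heard. Section 4.2 closes recruitment once 60 people pass the screening form, whereas section 5.4 puts consent, the medication and psychiatric screens and randomisation later. Section 8.1 does not say when its dropout occurs, so some losses may never be exposed.

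**What the gap leaves open.** Suppose all losses follow exposure and split equally, and no completer reports harm. The share harmed in an arm could then lie anywhere from 0/30 to 6/30 = 20%, or to 5/30 = 16.7% with 50 completers.

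**What recording could show.** With zero events among n people asked, the one-sided 95% upper bound is 1 − 0.05^(1/n).

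| People asked | n | Upper bound |
|---|---|---|
| All participants | 60 | 4.9% |
| One arm, all reply | 30 | 9.5% |
| One arm, completers (50 remain) | 25 | 11.3% |
| One arm, completers (48 remain) | 24 | 11.7% |

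**What it could not show.** The chance of at least one event among 30 is 1 − (1 − p)^30. This is 13.7% at p = 0.49%, 23.8% at 0.9%, 26.0% at 1% and 78.5% at 5%. An arm of 30 would usually show nothing at the cited rates, and a bound near 10% neither supports nor contradicts them.

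**The case against.** The strongest reply is that this is a disclosed and reasoned choice in a three-day audio study that needs IRB approval. Safety is not among the aims in section 2, and the omission does not bias the confirmatory STAI-6 comparison. That stands, and it is why the point is of low severity.

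A reader might also infer more than the documents support:

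- *That no event can be recorded at all.* Section 7.2 rules out systematic recording only, so an ad hoc note is possible. Section 7.4 lets a complaint arrive at any time, and participants are in contact with the coordinator by message.
- *That people who drop out leave no safety information.* STAI-6 and EMA items, including stressed, nervous and depressed, are taken before and after each track. Anyone who finishes a session leaves distress scores that can be linked to arm. What is missing is a definition of harm and a question about unwanted effects.
- *That people who feel worse are the ones who stop.* This is plausible, but the documents do not say it. The gap does not depend on it.
- *That the trials cited in section 3 recorded events systematically.* Section 3 gives the events reported, not how they were collected.
- *That section 7.2 bases low risk solely on not recording.* The same paragraph gives minimal risk and no medication as reasons first. The fault is a misplaced connective.

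**Conclusion.** The point holds as a cheap improvement, at low severity. No section gives an adverse event item, an exit contact or a safety table by arm, so the plan cannot produce a defined count by arm. That people who stop miss the end-of-trial feedback is inferred from its timing and from the lack of an exit step; it is not stated outright. Section numbering passes from 7.2 to 7.4, and if a section 7.3 exists it should be checked for a reporting step.

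The number not asked is at most about 10 to 12 of 60, on the assumption that all losses follow exposure. The bounds of 4.9% overall and 9.5% per arm assume zero events, a reply from everyone and 1:1 allocation. With completers only, the bound is about 11 to 12% per arm. The gain is honest descriptive reporting and information for planning the later trial. It is not evidence for the rates of about 1% in section 3, nor proof of safety.

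**What to change.** 1. Add to the Day 3 survey one closed item with free text asking whether the participant noticed any unwanted effect during or after the tracks.
2. Send the same item, with reply optional, through the existing message channel to randomised participants who stop early. Do this before phone numbers are deleted at the end of data collection. The access code allows replies to be matched to arm at analysis.
3. Add to section 8.2 a descriptive table of counts by arm, showing the number randomised and the number who answered, so that non-response is visible.
4. Reword the *Therefore* sentence in section 7.2 so that low expected risk rests on the minimal-risk reasoning and the literature in section 3, not on the decision not to record.

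The cost is one survey item, one standard message, a little coordinator time and an IRB notification. The tracks, the sample size and the confirmatory analysis are unchanged.
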